#### Did not initiate:

- Not eligible: Did not meet the criteria for eligibility of biologic therapy and did not initiate any therapy
- Eligible: Eligible for biologic therapy but did not initiate any biologic therapy
- A "frequent-eligibility" criterion of each biologic class will be used to assess eligibility. This
  criterion will be constructed using the results from the ISAR biologic availability survey and
  will be subject to confirmation from the ISAR scientific steering committee (see Table 1 for
  possible criteria per biologic class)

[figure not shown]

Table 1: Frequent-Eligibility Criteria per Biologic Class. Patients who did not initiate biologic therapy and are eligible will meet any of the three criteria for any of the three biologic groups.

	Anti-lgE	Anti-IL5/5R	Anti-IL4/13
Background therapy	Met via ISAR inclusion criteria		
Positive Allergen test	Yes, AND	N/A	N/A
IgE levels	≥ 30 IU/mL, AND	N/A	N/A
BEC	N/A	≥ 150 cells/µL with long- term OCS, OR ≥ 300 cells/µL without long-term OCS, AND	≥150 cells/µL with long-term OCS, OR ≥300 cells/µL without long-term OCS, OR
FeNO	N/A	N/A	≥25 ppb, AND
Exacerbation OR Iong-term OCS	Pre-therapy exacerbation (≥2) OR On long-term OCS	Pre-therapy exacerbation (≥2) OR On long-term OCS	Pre-therapy exacerbation (≥2) OR On long-term OCS

The ISAR enrolment date will mark the start of the outcome period for those who did not initiate biologics while for those who did the index date will be signified by the First Biologic Therapy Start Date. A minimum of 16-weeks of follow-up time post biologic initiation (outcome period) will be applied in alignment with the ERS recommendation for time of biologic response assessment [8]. This is also congruent with the methodology used in the ISAR research project 'Defining and Characterizing Responders to Biologic TrEAtment in Severe AsthMa Patients (BEAM).' To assess the impact of this design, the study will evaluate and report the number of patients that had three types of follow-up data: 1.) <24 weeks, 2.) > 24 weeks to 1-year 3.) >1-year.

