#### 3.2 STUDY OUTCOMES

The following outcomes measures are measured after index date (follow-up visits).

Table 3 Clinical outcomes of interest for objective 2 of the study

Variable Name	Туре	Description
Number of annualized asthma exacerbations 	Count	Annualized number of exacerbations requiring rescue steroids after index date
Asthma control in the past 4 weeks	Categorical	Categorized as controlled, partly controlled, or uncontrolled according to the GINA Asthma Control Criteria/Asthma Control Questionnaire (ACQ-6)/Asthma Control Test (ACT)
Total dose of oral corticosteroids 	Continuous	Label Dose X Frequency X Duration of Use for maintenance OCS between the index date and date of data extraction
Number of hospital admissions	Count	Annualized number of hospital admissions after index date
Number of emergency room visits	Count	Annualized number of emergency room visits after index date

<sup>3 Total number of exacerbations will be calculated between index date and current visit date

<sup>4 If use of SCS started after the index date, total dose will be calculated between start- and end date of use

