**Primary outcome: Exacerbation** 

An asthma exacerbation will be defined as the occurrence of the following events (ERS/ATS task

force definition):

asthma-related hospital attendance/admission primary care consultation; AND/OR

asthma-related A&E attendance; AND/OR

an acute oral corticosteroid course of 3 days or more

separate recordings of exacerbations within a 14 day period will be treated as the

same exacerbation.

A time-to-event analysis will be performed to analyse the association between utilization pattern and time to first exacerbation with right censoring at the time of death, switching, stopping or loss to follow-up. Kaplan-Meier curves will be used to describe event-free survival over time and comparisons. Conditional Cox regression will be performed with time to the first exacerbation as the outcome variable (y) to estimate Hazard Ratios (HR) with 95% confidence intervals (CI) of the main effect. The proportional hazard assumption will be evaluated visually by means of a log-log

plot of survival.

As the dispersion of the exacerbation data is expected to be high and as this outcome is conditional on the duration of follow-up, we may apply a negative binomial regression (NBR) to estimate the reduced rate of exacerbation (y=annual rate of exacerbation). We switch to a count model to take advantage of all exacerbations at follow up. Group comparisons (e.g. gender, BMI, number of biologics available etc.) will be made if interaction between a group and biologic use pattern is found. We will also run a NBR using the total post-therapy/post-ISAR enrolment

exacerbations.

Secondary outcome: Asthma control

By applying a multinomial regression model (ordered), we will assess the probability or odds of the combined categories partially or controlled versus uncontrolled asthma for those that continue

compared to those that do not initiate or switch or stop.

Secondary outcome: long term oral corticosteroid (OCS) dose

20

Study Protocol: [OPCG-2005] Biologic Usage Patterns, Clinical Outcomes and Healthcare Resource Utilization (CLEAR)

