#### Secondary outcome: Health resource utilization

Hospitalizations, invasive ventilations (if available) and emergency room visits will compose the outcome variable of health resource utilization (section 3.2). The difference in the number of incident hospital or emergency room visits in the outcome period across groups will be examined similarly to the primary outcome (exacerbation) discussed above. These outcomes will be considered separately for each healthcare resource and as a combined variable as well.

Study Protocol: [OPCG-2005] Biologic Usage Patterns, Clinical Outcomes and Healthcare Resource Utilization (CLEAR)

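### The exacerbation count models should be one negative binomial regression of the event count with log follow-up as offset: the protocol makes the annual rate the response of one model and names no offset for the total-count model

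*Protocol*

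**What the plan says.** The protocol's Section 4.2, under the primary outcome, first plans Kaplan-Meier curves and a conditional Cox regression of time to first exacerbation. It then turns to negative binomial regression (NBR), giving as reasons the expected overdispersion and the dependence on time observed: "as this outcome is conditional on the duration of follow-up". The stated purpose of that model is "to estimate the reduced rate of exacerbation (y=annual rate of exacerbation". The sentence that follows describes it as a count model. This model is worded as optional. A further one is worded as firm: "We will also run a NBR using the total post-therapy/post-ISAR enrolment" exacerbations. Neither sentence mentions an offset or exposure term.

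Table 3 in Section 3.2 gives the outcome the type Count but describes it as "Annualized number of exacerbations requiring rescue steroids after index date". Its footnote 3 adds: "Total number of exacerbations will be calculated between index date and current visit date". The window therefore differs from patient to patient. Section 2.2 expects "three types of follow-up data: 1.) <24 weeks, 2.) > 24 weeks to 1-year 3.) >1-year". Under health resource utilization, hospital and emergency visits "will be examined similarly to the primary outcome (exacerbation) discussed above".

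**The concern.** NBR models a whole-number count, and time at risk normally enters as an offset, the log of follow-up with its coefficient fixed at 1. The protocol recognises that follow-up matters, but neither model as written uses it in that way.

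With the annual rate as response, the variable is no longer an integer and the NBR mean-variance relation does not describe it. One event in 24 weeks enters as 2.17 per year and counts as much as a rate observed over several years.

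With the total as response and no offset, a group followed for longer accrues more events at the same underlying rate, and the model reports this as a group difference. Several features of the design make equal follow-up between groups unlikely:

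- The clock starts at biologic start for initiators and at registry enrolment for non-initiators (Section 2.2), and there is no common end date.
- The 1 January 2014 cut-off (Section 4.2) and data receipt before July 2021 (Section 2.1) allow up to about 7.5 years for initiators. Recruitment from December 2015 (Section 2.3) allows about 5.6 years for non-initiators.
- Continuers need at least 6 months on the first biologic, switchers may switch after any interval, and stoppers are to have an added period after stopping (Section 2.2). Group membership is thus tied to time observed.
- Matching on baseline characteristics does not by itself equalise follow-up.

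**Working it through.** **Figure to reproduce.** None. The readable text gives no event numbers, power or mean follow-up by group. The group sizes in Section 1 (2,791 continued, 356 stopped, 384 switched; 2,791 + 356 + 384 = 3,531) serve only to scale the simulations.

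**Annualising.** One event in 24 weeks: 52.18/24 = 2.17 per year. At the 16-week minimum also stated in Section 2.2 it would be 52.18/16 = 3.26. The 24-week minimum in Section 2.1 and the 16-week one need reconciling; 24 weeks (24/52.18 = 0.46 years) is used below.

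**What a total-count model without offset estimates.** For patient i in group g, E[events] = rate(g) × t(i). With a log link and a group indicator alone, the fitted ratio is the ratio of group means:

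ratio = [rate(1) × mean t(1)] / [rate(0) × mean t(0)]

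If the rates are equal, this is mean t(1) / mean t(0).

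**Simulations with a true rate ratio of 1.** Assumed, not in the documents: the event rate, a dispersion of 1 and the follow-up ranges. Rows A to D use 356 patients per group, 1.5 events per year and 300 runs. Row E uses 2,791 versus 384 patients, 1 event per year and 200 runs. The ratio is the second group over the first.

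| Follow-up, first vs second group | Ratio of mean follow-up | Total, no offset: ratio (rejection) | Annual rate: ratio (rejection) | Count with offset: ratio (rejection) |
|---|---|---|---|---|
| A: both 0.46–3 y | 1.00 | 1.00 (5.0%) | 1.00 (6.3%) | 1.00 (4.7%) |
| B: 0.46–3 y vs 0.46–1.5 y | 0.98/1.73 = 0.57 | 0.57 (100%) | 1.00 (7.0%) | 1.00 (6.7%) |
| C: 1 y vs 0.46 y | 0.46 | 0.47 (100%) | 1.01 (2.7%) | 1.01 (5.0%) |
| D: means 2.0 y vs 1.6 y | 1.6/2.0 = 0.80 | 0.79 (66%) | 0.99 (5.0%) | 0.99 (4.7%) |
| E: 0.46–3 y vs 0.46–5 y | 2.73/1.73 = 1.58 | 1.56 (100%) | 0.995 (6.5%) | 0.995 (5.5%) |

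The total-count ratio follows the ratio of mean follow-up in every row. The rejection rates of the other two models lie within simulation error of 5%: with 300 runs, 5% ± 1.96 × √(0.05 × 0.95/300) is 2.5% to 7.5%.

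**Precision of the annual-rate response.** The scenarios run at 1 event per year gave a variance 1.05 to 1.15 times that of the offset model. In rows A to D the squared ratios of empirical standard errors are (0.089/0.087)² = 1.05, (0.101/0.102)² = 0.98, (0.107/0.107)² = 1.00 and (0.091/0.090)² = 1.02. The loss is real in principle and small here.

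**Total count with equal follow-up.** Row A shows no false effect, but omitting the offset still costs precision: (0.095/0.087)² = 1.19.

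**The case against.** The strongest reply is that only the annual-rate response is explicit, and that it does little harm: the ratio stays essentially unbiased. That stands. The fault there is one of weighting, variance and model form.

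For the total-count model, the protocol names a response and is silent on exposure. An analyst could well add follow-up time, and such an option is often left to the analysis plan, which is not at hand. That stands too: the text names no offset but does not exclude one. It does not remove the point. If an offset is intended, the second model is already the right rate model and the first is redundant. If none is intended, the second is wrong. The wording needs changing in both cases.

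A reader might infer that the total-count model will produce a false group effect, or that 1.56 is the bias to expect. The documents do not support this. A false effect needs mean follow-up to differ between the compared groups, and no follow-up by group is reported. Both its size and its direction come from the assumed ranges.

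The count models also stand beside a Cox analysis of the same outcome, in which censoring takes account of unequal follow-up. Finally, the health resource section says only that its analysis is similar, and Table 3 defines admissions and emergency visits as annualised numbers. A raw-total model for these is possible but not stated.

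**Conclusion.** The point holds in a limited form. The protocol explicitly makes the annual rate the response of an NBR, and it names no follow-up offset for the NBR of total exacerbations, although it recognises that the outcome depends on follow-up and counts events over patient-specific windows.

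The explicit defect costs some precision: up to about 15% in variance in the scenarios tried, and close to nothing in several. The larger risk is conditional on two things: the total-count model being run without an offset, and mean follow-up differing between groups. The design makes the second likely but does not quantify it. If both hold, the estimated ratio is multiplied by the ratio of mean follow-up. Means of 1.6 versus 2.0 years would be enough to give 0.79 and a 66% false rejection rate at 356 patients per group, under the assumed event rate and dispersion. With equal follow-up there is no false effect. The time-to-first-exacerbation analysis is untouched. This is an inexpensive correction to make before the analysis, not a flaw that invalidates the plan.

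**What to change.** In Section 4.2, replace the two NBR statements with one: the response is the number of exacerbations in the observed period, modelled by negative binomial regression with log(person-years observed) as offset, and annualised rates and rate ratios are reported as model output. Use the same form wherever hospital admissions and emergency visits are analysed as counts. In Table 3, record the number of events and the person-time observed as the analysis variables, and keep the annualised figure for description.

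Reporting the distribution of follow-up by utilization group, beside the follow-up categories already planned in Section 2.2, would show how unequal it is. The cost is one sentence in the protocol and one option in the Stata command. No new data are needed, because the planned annualisation already requires each patient's follow-up time.

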One of the promising ways of addressing all the severe asthma phenotypes may be via targeting one of the upstream inflammatory responses of the disease, such as the cytokine thymic stromal lymphopoietin (TSLP)[13]. TSLP is expressed by the airway epithelium in response to both allergic and non-allergic eosinophilic inflammation [14]. Lack of effective therapies for all patients with severe asthma, together with additional hurdles, such as accessibility or eligibility for more

Study Protocol: [OPCG-2005] Biologic Usage Patterns, Clinical Outcomes and Healthcare Resource Utilization (CLEAR)

than one biologic, have led to patients receiving sub-optimal or inappropriate biologics at initiation [11,12]. This can lead to various patterns of use, such as stopping or switching from the first biologic to a second, and in some cases, to a third or fourth biologic as clinicians and patients search deliberately for adequate response.

In an ISAR study on Biologic Utilization (prepublication) most patients (79%; 2791/3531) continued their first biologic, 10% (356/3531) stopped and 11% (384/3531) switched among patients who were followed up for at least a period of 6 months. This pattern was reproduced at the country level, although the ratio of 'stoppers' to 'switchers' varied. The most common reported reasons for stopping or switching a biologic was lack of efficacy benefits and/or adverse events. Disruption to the clinical management of biologics, most likely due to ineffective response and/or inappropriate initiation of the , may lead to a worsening of asthma control and an associated increase in health care utilization. This has yet to be demonstrated in a real-world setting or quantified. In addition, there may be a subgroup that is eligible yet is not reaping the benefits of targeted therapy.

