First the demographic and clinical characteristics as mentioned in section 3.1 will be described in detail per group. This will include describing proportions on patients from each group based on their biomarkers, long term OCS (LTOCS) use, baseline demographics such as those outlined in Section 3.1. Next, the significant difference in level of T2 phenotypes and demographic or clinical characteristics (section 3.1) across the five groups will be compared and tested for statistical significance via Chi-square tests for comparison of counts data, and t-test or one-way analysis of variance (ANOVA) for continuous variables. Where appropriate, McNemar tests, paired t-tests will be considered. Statistical significance will be defined as p <0.05. Stata version 14.2 (College Station, TX, USA) will be used to conduct all statistical analyses and data manipulations.

Additionally, comparisons will be made as follows:

Study Protocol: [OPCG-2005] Biologic Usage Patterns, Clinical Outcomes and Healthcare Resource Utilization (CLEAR)

- 1. Switch vs. continue
- 2. Stop vs. continue
- 3. Patient received biologics vs. eligible but did not receive biologics
- 4. Biologic eligible (biologic users+ non-users but who qualify) vs. not eligible.

#### 4.2 OBJECTIVE 2

As there are various factors underpinning the probability of not receiving, receiving, continuing, switching, or stopping a biologic, comparing the clinical outcomes set forth in section 3.2 will need careful consideration. One of the main confounders to consider is the availability and/or accessibility of multiple biologics in a country. Therefore, all countries included in the analysis of assessing the clinical outcomes across biological utilization groups will have at least 2 biologics available in the market (availability defined as licensed in the country) at the time of the patient's enrolment into ISAR (index date). There will be a cut-off date of 01 Jan 2014 for assessment of clinical outcomes to ensure the availability of drugs in the market.

Furthermore, according to the results of objective 1 (pre-therapy or baseline characteristics), before assessing for differences in the clinical outcomes across groups, baseline imbalance will be examined across groups and matched accordingly. Prior to this step, the clinical outcomes of each group will be described.

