#### **Group comparisons**

The first set of results for the primary and secondary outcomes (section 3.2) will be demonstrated for those that did not initiate a biologic versus those that did (switch, stop, continue) (initiators

Study Protocol: [OPCG-2005] Biologic Usage Patterns, Clinical Outcomes and

Healthcare Resource Utilization (CLEAR)

versus non-initiators). The second set of results will compare the outcome results for patients that stopped or switched versus those that continued.

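### The asthma-control analysis sets continuers alone against non-initiators, a contrast that the protocol's own group comparisons do not list and that selects on status after index

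*Protocol*

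**What the plan says.** Protocol section 4.2, under Group comparisons, fixes the contrasts for the outcomes. "The first set of results for the primary and secondary outcomes (section 3.2") are for "those that did not initiate a biologic versus those that did (switch, stop, continue"), so everyone who started a biologic stays on the treated side. Then: "The second set of results will compare the outcome results for patients that stopped or switched versus those that continued". Asthma control is listed in section 3.2 (Table 3) and is labelled a secondary outcome in section 4.2, so both contrasts cover it.

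The paragraph on asthma control in section 4.2 specifies an ordered regression for partly or fully controlled "versus uncontrolled asthma for those that continue", "compared to those that do not initiate or switch or stop".

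Two other places bear on this. Section 2.2 defines a continuer by at least six months on the first biologic with no sign of stopping or switching. The Background reports from an earlier ISAR study: "The most common reported reasons for stopping or switching a biologic was lack of efficacy benefits and/or adverse events".

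**The concern.** The asthma-control sentence names continuers as the index group and includes non-initiators among the comparators. The Group comparisons text has no such pairing. An analyst who follows the asthma-control sentence alone would not produce the contrast of all initiators with non-initiators for this outcome.

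The substitution matters because continuing is not a baseline characteristic. It is established over the months after index and, by the Background, depends largely on how the first biologic worked or was tolerated. Taking stoppers and switchers out of the treated side removes initiators for reasons tied to response, and nothing equivalent happens among non-initiators. The matching and standardized-difference checks in section 4.2 use baseline variables, so they cannot correct a selection that arises later. An odds ratio from this contrast could be reported as a benefit of biologics when part of it comes from the way the group was formed.

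The phrase also permits two analyses: three separate odds ratios with continuers as the reference, or one odds ratio against a merged comparator. They mean different things.

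**Working it through.** **The plan's own figure.** The Background gives 2791 continued, 356 stopped and 384 switched. The sum is 3531, and the shares are 79.04%, 10.08% and 10.88%, which match the stated 79%, 10% and 11%. Stoppers plus switchers are 740/3531 = 20.96%.

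**Contrasts side by side.**

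| Pairing | Group comparisons | Asthma-control sentence |
|---|---|---|
| All initiators vs non-initiators | yes | not mentioned |
| Stopped or switched vs continued | yes | yes (pooled or separate not stated) |
| Continuers vs non-initiators | no | yes |

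**Illustration of the selection effect.** The protocol gives no control rates and no count of non-initiators that could be used here, so these are assumptions. Let p1 be control in all initiators, p0 in non-initiators and ps in stoppers and switchers. Control in continuers follows from the split:

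pc = (p1 − 0.2096 × ps) / 0.7904

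OR (continuers vs non-initiators) = [pc/(1 − pc)] / [p0/(1 − p0)]

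*No effect of initiation, p1 = p0 = 0.40.* All initiators versus non-initiators gives OR 1.00 in every row.

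| ps | pc | OR, continuers vs non-initiators |
|---|---|---|
| 0.40 | 0.400 | 1.00 |
| 0.30 | (0.40 − 0.0629)/0.7904 = 0.427 | 1.12 |
| 0.20 | (0.40 − 0.0419)/0.7904 = 0.453 | 1.24 |

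Over a wider assumed range (p1 = p0 from 30% to 60%, ps at 0.8 to 0.4 times that rate), the OR runs from 1.08 to 1.52 with no true effect.

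*True benefit, p0 = 0.40, p1 = 0.55.* For the pooled reading, let M be the number of non-initiators, with ppool = (M × p0 + 740 × ps)/(M + 740). M is taken as 500 to 2000.

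| ps/p1 | All initiators vs non-initiators | Continuers vs non-initiators | Continuers vs pooled comparator |
|---|---|---|---|
| 1.0 | 1.83 | 1.83 | 1.27–1.55 |
| 0.8 | 1.83 | 2.06 | 1.87–1.97 |
| 0.6 | 1.83 | 2.33 | 2.52–2.78 |

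Continuers versus non-initiators exceeds the all-initiators result whenever stoppers and switchers do worse, and equals it when they do not differ. The pooled comparator can fall on either side: it understates in the first row and overstates in the other two.

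**The case against.** The strongest reply is that the asthma-control sentence adds a comparison and withdraws nothing. Group comparisons covers the secondary outcomes, so all initiators versus non-initiators can still be regarded as planned for asthma control. Continuers versus stoppers or switchers is the second listed contrast, and describing outcomes across usage patterns is Objective 2. This stands in part. It would be wrong to infer that the protocol has dropped the initiator contrast, or that the whole sentence conflicts. Only the continuers versus non-initiators pairing does. But this is the only model sentence for the outcome, and it leaves out the contrast that the section puts first.

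Three stronger inferences are tempting and are not supported.

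- *That stoppers and switchers are pooled with untreated patients.* The text does not say so. Continuers as the reference against each group separately fits equally well.
- *That the result must overstate benefit.* This requires worse follow-up control in stoppers and switchers, for which the protocol gives no figure. Control covers the past 4 weeks, and switchers may be on a second biologic by then. Adverse events are also among the reasons for leaving. Under pooling, a true benefit can be understated.
- *That non-initiators are an unselected group.* Section 2.2 divides them into eligible and not eligible, so they carry selection of their own. Section 4.2 acknowledges such factors and plans matching. The net bias against this group cannot be derived from the protocol.

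It is also fair to say that stopped or switched versus continued conditions on the same post-index status. Following Group comparisons does not make that contrast causal.

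**Conclusion.** The point holds in a limited form. The asthma-control sentence uses a continuers versus non-initiators contrast that Group comparisons does not list, and it does not say whether its comparators are separate or pooled. That contrast selects initiators on post-index status related to efficacy and tolerability, and baseline matching leaves this untouched.

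Overstatement is likely but conditional: it occurs if stoppers and switchers have worse control than continuers. The illustrative size with no true effect is OR 1.12–1.24. It rests on the earlier study's 79/21 split, an assumed 40% control in initiators and non-initiators, an assumed 20–30% in stoppers and switchers, and no other difference between initiators and non-initiators. The actual size cannot be obtained from the protocol, and for a pooled comparator neither can the direction. This is a secondary outcome and the correction is small, so the sentence should be changed, but the study design is not in question.

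**What to change.** In the asthma-control paragraph of section 4.2, state that the outcome uses the two contrasts under Group comparisons:

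1. All initiators (switch, stop and continue together) versus non-initiators, as the estimate for starting a biologic.
2. Stopped or switched versus continued, interpreted as an association because group status arises after index. Separate odds ratios for stopping and for switching are preferable. This is a refinement of the plan: the separate listing ("Stop vs. continue" and its switch counterpart) appears in section 4.1 for Objective 1, not for outcomes.

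Add that non-initiators are not pooled with stoppers or switchers, and that any continuers versus non-initiators result is labelled descriptive.

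The cost is a short change of wording, with the same data and the same model. The asthma-control estimate may become less favourable.
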